### 8.3.3.1 Instructions for Supervised Confinement for V6 and V9

Beginning at breakfast (the first meal) on Day 1 of the supervised confinement, patients will be placed on a 72-hour controlled diet, with 100 g fat/day (3 meals and 2 snacks per day) and a minimum of 1.5 to 2 g of protein per kg of body weight. Although it is preferred to have the patient consume exactly 100 g of fat per day, the fat excretion assay remains valid with a fat intake range within 15% of the goal (ie, 85 to 115 g of fat per day). The nutritional planning and calculation of dietary fat and nitrogen (protein) intake will be conducted by a qualified dietitian at each site. The actual fat and nitrogen (protein) intake will be calculated from the recorded type and amount of food consumed. A central laboratory will calculate CFA, CNA, and stool weight values on the basis of dietary intake and the fat and nitrogen excreted in stool.

An indicator marker (500 mg of Food, Drug, and Cosmetics [FD&C] Blue #2) will be provided as two 250-mg capsules. The first marker (consisting of two 250-mg capsules) will be given at the beginning of breakfast or first meal on Day 1 of the supervised confinement to mark the start of the controlled diet. The second marker (two 250-mg capsules) will be given at the beginning of breakfast or first meal on Day 4 to mark the end of the controlled diet. Stool collection for fecal fat and nitrogen assessments must begin after the first marker has passed (the first stool containing the first marker is discarded) and is completed when the second marker has passed (the first stool containing the second marker is collected). Patients must continue the supervised confinement until the second stool marker is passed. The controlled diet will be maintained until the patient takes the second marker. Although it is not part of the controlled diet, the breakfast or first meal consumed on Day 4 of the supervised confinement should mimic (as closely as possible) the breakfast or first meal consumed on Day 1 of the supervised confinement.

If the patient has not passed the first blue dye marker within 4 days after ingesting the first dye marker capsules, or within 2 days after ingesting the second dye marker capsules, then 5-10 mg of oral bisacodyl may be given. Bisacodyl is the only laxative that may be given during the marker-to-marker stool collection period. Note: Patients on a stable chronic osmotic laxative may continue this therapy during the marker-to-marker stool collection.

The supervised confinement may take place within an inpatient facility or within an alternative confinement setting. This will be discussed and approved on an individual case basis by the sponsor. The alternative confinement setting will require the supervision of trained study site staff to oversee the study procedures.

## 9. SAFETY ASSESSMENTS

The planned Schedule of Assessments is included in [Section 7.1.1 \(Table 1\)](#).

### 9.1 Definitions

#### 9.1.1 Adverse Event

An AE is any untoward medical occurrence experienced by a patient in a clinical investigation; it does not necessarily have a causal relationship with this study drug. An AE can therefore be any unfavorable and unintended sign, symptom, or disease temporally associated with the use of a medicinal product, whether or not considered related to the medicinal product.

Active or worsening of EPI is not considered an AE for the purposes of this study. Worsening of EPI disease should not be recorded as an AE, but should be recorded in the appropriate EPI CRF.

Adverse events may also include postdose complications that occur as a result of protocol-mandated procedures (eg, invasive procedures such as venipuncture, biopsy, etc.). Preexisting events that increase in severity or change in nature during, or as a consequence of, use of a medicinal product in a human clinical study will also be considered AEs. Any preexisting medical condition or diagnosis associated with a clinically significant laboratory abnormality should be documented on the CRF or eCRF. The Investigator should attempt to establish a diagnosis of the event based on signs, symptoms, and other clinical information. In such cases, the unifying diagnosis should be documented as the AE, rather than the individual signs and symptoms (eg, runny nose, scratch throat, cough, and low grade fever should be recorded as a upper respiratory infection and not each of the individual symptoms).

An AE does NOT include the following:

- Medical or surgical procedures (eg, surgery, endoscopy, tooth extraction, transfusion); the condition that necessitates the procedure is an AE
- Any preexisting disease or condition or laboratory abnormality present or detected before the start of administration of study medication that does not worsen
- Laboratory abnormalities without clinical manifestations, which do not require medical intervention, or that do not result in termination or delay of study medication

- Situations where an untoward medical occurrence has not occurred (eg, hospitalization for elective surgery, social, or convenience admissions)
- Overdose of any study drug or concomitant medication without any signs or symptoms, unless the patient is hospitalized for observation
- Worsening and/or flares of EPI disease activity. This should be recorded in the appropriate EPI CRF. However, if disease worsening meets any of the criteria for an SAE, it must be recorded on the SAE form and reported to the Sponsor or designee within 24 hours of becoming aware of the event.

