## 6. STUDY OBJECTIVES

### 6.1 Primary Objectives

The primary objectives of this study are to assess the safety and efficacy of MS1819-SD vs porcine PERT in patients with EPI due to CF.

The primary safety objective of the study is to assess the safety and tolerability of a dose of 2240 mg/day of MS1819-SD in patients with EPI caused by CF. Efficacy will be evaluated by comparing treatment with MS1819-SD to treatment with porcine PERT.

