4.1 Modified Intent-to-Treat Population

The modified intent-to-treat (mITT) population includes all randomized subjects who receive at least 1 dose of treatment and have at least 1 sufficient stool sample. A stool sample will be considered sufficient if the date and time associated with the second blue dye marker is recorded, indicating that the stool sample collection is complete. The mITT will be used for efficacy analyses. Subjects will be analyzed according to the treatment group to which they were randomized regardless of the actual treatment received, unless stated otherwise.

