9.2.2.2 Stool Weight

Stool weight during the 72-hour marker-to-marker stool collections will be evaluated at the end of each treatment period (Visit 6, Visit 9). All collected stool will be shipped to the central lab for determination of the stool weight as described under the primary efficacy measure.

Stool weight at the end of each treatment period will be analyzed from stool samples collected during the 2 confinement periods (Visit 6 and Visit 9).

Stool weight at the end of each treatment period (Visit 6, Visit 9) will be summarized by treatment group using descriptive statistics. If a subject switches study treatments (i.e. MS1819 to PERT or PERT to MS1819) during the confinement period, prior to the end of the stool collection, then the stool weight value during that confinement period will be excluded from the summary.

If a subject has more than one stool weight record for a given visit (Visit 6 or Visit 9), only the heaviest value will be included in the summary.

Stool weight will be listed by visit for all subjects in the mITT population.

9.2.2.3 *Malabsorption Signs and Symptoms*

Signs and symptoms of malabsorption will be evaluated at Visits 3, 4, 5, 6, 7, 8, 9, and 10.

The EPI malabsorption symptoms will be evaluated according to the following measures:

- Stool frequency (number of bowel movements per day);
- Stool consistency (graded as 0 = hard, 1 = formed/normal, 2 = soft, 3 = watery, or 4 = overt diarrhea);
- Bloating (graded as 0 = none, 1 = mild, 2 = moderate, or 3 = severe);
- Abdominal pain (graded as 0 = none, 1 = mild, 2 = moderate, or 3 = severe);
- Flatulence (graded as 0 = none, 1 = mild, 2 = moderate, or 3 = severe);
- Incidences of visible oil/grease in stool (Yes/No).
- Increased stool quantity (graded as 0 = none, 1 = mild, 2 = moderate, or 3 = severe); and
- Worsening of overall bowel habit (graded as 0 = none, 1 = mild, 2 = moderate, or 3 = severe).

Stool frequency will be summarized by treatment group for the mITT population using descriptive statistics. Stool frequency will be summarized at Visit 3 (At Randomization), At First Dose, 1 Week Post First Dose, 2 Weeks Post First Dose, and 3 Weeks Post First Dose, as described in Section 3.

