The number and percentage of subjects within each category for stool consistency, bloating, abdominal pain, flatulence, incidence of visible oil/grease in stool, increased stool quantity, and worsening of overall bowel habit at each study visit and by treatment group will also be provided Visit 3 (At Randomization), At First Dose, 1 Week Post First Dose, 2 Weeks Post First Dose, and 3 Weeks Post First Dose, as described in Section 3. Shifts from Visit 3 will be presented for stool consistency, bloating, abdominal pain, flatulence, increased stool quantity, and worsening of overall bowel habit for the mITT population by treatment group.

Signs and symptoms of malabsorption will be listed for all subjects in the mITT population.

9.2.2.4 *Weight and BMI*

Weight and BMI will be evaluated at Visits 1, 3, 6 and 9.

Weight and BMI at Visit 3 (At Randomization), At First Dose, and at 3 Weeks Post First Dose, as described in Section 3, will be summarized for the mITT population using descriptive statistics by treatment group.

Weight and BMI will be listed for all subjects in the mITT population.

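### An MS1819-first patient who leaves before completing the Visit 6 stool collection because of non-serious EPI worsening has no planned AE, malabsorption or CFA output

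*Protocol*

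**What the plan says.** Tolerability is part of a primary objective. Protocol 6.1 states: "The primary safety objective of the study is to assess the safety and tolerability of a dose of 2240 mg/day of MS1819-SD". SAP 8.1 plans safety summaries by actual treatment so that MS1819 and PERT can be compared within patients.

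On adverse events, Protocol 9.1.1 states: "Active or worsening of EPI is not considered an AE for the purposes of this study". Its list of what is not an AE repeats this: "Worsening and/or flares of EPI disease activity. This should be recorded in the appropriate EPI CRF". The exception follows at once: "However, if disease worsening meets any of the criteria for an SAE, it must be recorded on the SAE form".

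On malabsorption, SAP 9.2.2.3 states: "Stool frequency will be summarized by treatment group for the mITT population using descriptive statistics". The shift tables are also for mITT. The category counts name no set, but SAP 4.1 makes mITT the set for efficacy analyses. On the listing: "Signs and symptoms of malabsorption will be listed for all subjects in the mITT population".

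SAP 4.1 defines mITT as the population that "includes all randomized subjects who receive at least 1 dose of treatment and have at least 1 sufficient stool sample". A sample is sufficient when the date and time for the second dye marker are recorded.

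**The concern.** Patients enter stable on PERT, and one period takes them off it. Worsening malabsorption on MS1819 is therefore a foreseeable consequence of the switch as well as a feature of the background disease. The protocol says as much. Section 7.1 notes that symptoms can appear within days of moving from PERT to an investigational lipase, and section 10.2 expects CFA to be about 8 points lower on MS1819.

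With non-serious worsening outside the AE tables, the malabsorption outputs have to carry this information. They are restricted to patients who lasted long enough to complete a stool collection. In the MS1819-first sequence, the patients removed by that restriction include any who left early because they tolerated the switch badly. The PERT period continues the prestudy treatment, so losses for this reason would be expected mainly on MS1819 and would make its tolerability look better than it was.

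**Working it through.** The question is which planned outputs would record the event. Most of the check sets the rules side by side.

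**The patient in question.** Randomised to MS1819 then PERT, takes at least one dose, has non-serious worsening of EPI, and leaves the study before completing the Visit 6 collection (Day 17 ± 7, Protocol 8.2.3).

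**Data scheduled.** Symptom grades at Visit 4 (about Day 8) and Visit 5 (about Day 15) under Protocol 8.2.2, and at Early Withdrawal under Protocol 8.3.3. Early Withdrawal falls about 2 weeks after the last dose, so the Visit 4 and 5 grades are the ones that describe symptoms on MS1819. Someone who leaves before Visit 4 has no scheduled on-treatment grade.

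**Outputs that would not record the worsening.**
- TEAE tables, including TEAEs leading to discontinuation (SAP 8.3, 8.4): the event is not an AE.
- Malabsorption summaries, shifts and listing (SAP 9.2.2.3): the patient is not in mITT.
- CFA (SAP 9.1.1, 9.2.1): the value is missing and is not replaced.

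**Outputs that show the exit.**
- Disposition (SAP 5.1): withdrawals by period and reason, by sequence, for all randomised patients, with a listing.
- Exposure (SAP 8.2): time on treatment, and first and last dose dates, for the safety population.

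**Neighbouring cases that are covered.**
- Worsening that meets an SAE criterion is reported (Protocol 9.1.1, 9.1.2) and tabulated for the safety population (SAP 8.4).
- A PERT-first patient with a complete Visit 6 collection who leaves MS1819 in period 2 is already in mITT, so recorded symptoms are listed.
- A patient who stops MS1819 but stays in the study and completes any collection is in mITT.

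**Protocol against SAP.** Protocol 7.3.4 keeps treated early leavers in the ITT efficacy analysis, and Protocol 10.3 uses ITT for all efficacy endpoints. The protocol's own set would have included this patient. SAP 4.1 does not, the SAP takes precedence (SAP section 1), and SAP 11.1 does not list the change.

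**How many.** The plan's enrolment figure reproduces: 30 / (1 − 0.20) = 37.5, rounded up to 38. Expected dropouts are 38 − 30 = 8, or 8/38 = 21%. The documents do not split these by sequence, period, treatment or reason. As an illustration only, suppose a share of the 8 leave while on MS1819 and a share of those leave in period 1 without a complete collection:
- shares of 50% and 50%: 8 × 0.5 × 0.5 = 2 patients;
- shares of 75% and 75%: 8 × 0.75 × 0.75 = 4.5 patients;
- shares of 100% and 100%: 8 × 1 × 1 = 8 patients.

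Each count further assumes that the reason was non-serious EPI worsening. Nothing in the documents rules out 0.

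**The case against.** The strongest reply is that a reader might infer that this harm vanishes from every safety and efficacy output, and the documents do not support that. Dropouts are a named safety endpoint (Protocol 7.2.3), disposition with reason covers every randomised patient, exposure covers the safety population, and serious worsening is tabulated. Most patients who leave in period 2 stay in mITT. This stands, and it limits the point to one subgroup.

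Two further inferences rest on forms that are not in the documents:
- One is that worsening sent to the EPI CRF is never reported. The SAP names no output from that form, but the form is not defined. It may be the one that holds the malabsorption grades, and the table and listing specifications are separate documents.
- The other is that the disposition table cannot show loss of effect because Protocol 7.3.4 does not list it. That section gives reasons for which a patient may be withdrawn; it is not shown to be the CRF code list, and it requires the reason to be fully documented.

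It can also be said that routing the treated condition to efficacy forms is a legitimate design choice. That is accepted, and the AE definition need not change. The choice does, however, require the efficacy forms to be reported for everyone treated. Disposition and exposure show that a patient left and when. At best the reason field says why, and neither output shows the symptom grades.

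**Conclusion.** The point holds for a defined subgroup: MS1819-first patients who leave the study before completing the Visit 6 collection because of non-serious EPI worsening. For them no AE, malabsorption or CFA output is planned, and any symptom grades collected go unreported. Disposition and exposure are the only planned outputs that show the exit.

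The size is unknown. Within the plan's allowance of about 8 dropouts it is anywhere from 0 to 8. A reader might quote the upper end as 8 of about 19 MS1819-first patients (38/2), or 42%. That requires every expected dropout to be in that sequence, before a complete Visit 6 collection and for this reason, and the documents support none of these. Any loss would probably favour MS1819; this rests on the protocol's own expectation of a lower CFA and early symptoms after the switch. The gap is modest and cheap to close, and it matters because tolerability is a primary objective.

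**What to change.** - In SAP 9.2.2.3, summarise and list malabsorption signs and symptoms by actual treatment for the safety population, and keep the mITT version as an extra. The summary would then include the Visit 4 and 5 grades of early leavers, and the listing would include Early Withdrawal.
- In the SAP safety outputs, include any worsening of EPI recorded on the EPI CRF, by treatment, with the number who discontinued.
- If the disposition CRF lacks it, add worsening of EPI / loss of effect as a recorded withdrawal reason. This concerns what is recorded; it does not change any rule for stopping treatment.

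The AE definition stays as it is, and the malabsorption grades are already scheduled. The cost is one or two extra outputs and possibly one reason code. The MS1819 tolerability profile may look slightly less favourable.

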## Criteria for Evaluation

### Safety endpoints:

AEs, SAEs, drop outs, and laboratory values.

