## 7.2 Study Endpoints

### 7.2.1 Primary Efficacy Endpoints

Safety and efficacy will be primary endpoints. Safety will be evaluated by descriptive methods. Efficacy will be assessed by noninferiority of CFA, between the MS1819-SD treatment vs the porcine PERT treatment.

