### 7.2.3 Safety Endpoints

AEs, SAEs and drop outs.

In addition, laboratory test results will be summarized ([Section 15.2](#)):

- Hematology
- Biochemistry
- Fasting lipid profile
- Urinalysis
- Serum MS1819 concentrations
- Antibodies against LIP2 lipase

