## 9.2 Reporting Procedures for All Adverse Events

AEs will be recorded in the CRF for all patients from the time the patient signs the informed consent form through the end of the study or patient withdrawal.

The Investigator is responsible for ensuring that all AEs (as defined in [Section 9.1](#) and as further specified below) observed by the Investigator or reported by patients are collected and recorded in the patients' medical records, in the CRF, and as an SAE in the electronic data capture system. These AEs will include the following:

1. All SAEs (as defined in [Section 9.1.2](#)) that occur.
2. All nonserious AEs (as defined in [Section 9.1.1](#)) that occur.

The following AE attributes must be assigned by the Investigator:

- AE diagnosis or syndrome(s) (if known, signs or symptoms if not known);
- event description (with detail appropriate to the event);
- dates of onset and resolution; severity; assessment of relatedness to study drug; and
- action taken with study medication.

The Investigator may be asked to provide follow-up information, discharge summaries, and extracts from medical records or CRFs.

It will be left to the Investigator's clinical judgment to determine whether the relatedness of an AE, and of sufficient severity to require the patient's removal from treatment or from the study. A patient may also voluntarily withdraw from treatment because of what he or she perceives as an intolerable AE. If either of these situations arises, the patient should be strongly encouraged to complete the End-of-Therapy assessments and be under medical supervision until symptoms cease or the condition becomes stable.

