## **9.7 Hepatic Monitoring**

The following guidelines are provided for the management of serum transaminase elevations in patients with new, clinically-meaningful increases in liver function tests occurring during the study. All cases of new (ie, since screening) elevations in ALT or AST  $\geq 3$  times ULN or any questions concerning the management of a patient with elevated serum transaminases should be discussed with the study Medical Monitor.

---

Patients who experience a new (ie, since screening) elevation in ALT or AST level to  $\geq 3 \times$  ULN OR total bilirubin  $\geq 1.5 \times$  ULN will have hepatic monitoring until one of the following occurs:

- Withdrawal from study if elevation in ALT or AST level to  $\geq 3 \times$  ULN is associated with a rise in total serum bilirubin to  $\geq 2 \times$  ULN (without laboratory findings of cholestasis [elevated serum alkaline phosphatase  $\geq 2 \times$  ULN])
- Withdrawal from study if elevation in ALT or AST level to  $\geq 5 \times$  ULN is associated with new or exacerbated gastrointestinal (GI) symptoms (ie, nausea, vomiting, right upper quadrant pain, and/or jaundice) and other causes are not evident
- Withdrawal from the study if elevation in ALT or AST is  $\geq 10 \times$  ULN regardless of serum bilirubin level

Causes of acute elevation of transaminases should be considered and ruled out (e.g., viral hepatitis, concomitant medications).

Patients discontinued from study drug administration should resume porcine PERT therapy according to physician prescription.

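### The *or* in the laboratory exception of Protocol 9.1.1 means an asymptomatic abnormality need not be an AE even if it needs treatment or stops study drug

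*Protocol*

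**What the plan says.** Protocol 9.1.1 opens broadly: "An AE is any untoward medical occurrence experienced by a patient in a clinical investigation". It then lists items that are not AEs, among them: "Laboratory abnormalities without clinical manifestations, which do not require medical intervention, or that do not result in termination or delay of study medication". A neighbouring item removes medical and surgical procedures from the definition but adds that "the condition that necessitates the procedure is an AE".

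Protocol 9.2 builds collection on that definition; its second category is "All nonserious AEs (as defined in" Section 9.1.1). SAP 8.1 and 8.3 derive TEAEs from the AEs so recorded and add no laboratory rule. SAP 8.4 tabulates TEAEs leading to study discontinuation.

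Protocol 9.7 deals with liver tests. It begins with "All cases of new (ie, since screening) elevations in ALT or AST" at or above 3 times ULN, and it includes withdrawal for ALT or AST at or above 10 times ULN whatever the bilirubin. That criterion does not require symptoms.

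On the standing of safety, Protocol 7.2.1 says "Safety and efficacy will be primary endpoints. Safety will be evaluated by descriptive methods". The Synopsis gives the safety endpoints as "AEs, SAEs, drop outs, and laboratory values", and Protocol 7.2.3 adds "In addition, laboratory test results will be summarized".

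**The concern.** An exception for laboratory findings normally serves to keep trivial results out of the AE listing, and for that all of its conditions need to hold at once. Joined with *or*, one favourable feature can be enough to remove a finding that is unfavourable in another respect. A finding serious enough to be treated, or to end treatment, can then be classified as no AE at all.

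Two things are at stake. First, AE and TEAE counts are a main part of a co-primary safety assessment that is purely descriptive, so the counts are the result. Second, the trial is planned for about 15 sites and about 38 enrolled patients. If some sites apply the sentence literally and others read it as cumulative, like events will be recorded differently, and in a sample of this size a few records visibly change a rate.

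**Working it through.** No planned figure depends on this wording, so the check is one of logic. Let S = clinical manifestations present, M = medical intervention needed, T = study drug terminated or delayed. The sentence can be parsed in three ways that keep the *or*:

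- P1: excluded if not S, or not M, or not T
- P2: excluded if not S, and (not M or not T)
- P3: excluded if (not S and not M), or not T

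The comparison is the cumulative rule, excluded only if not S and not M and not T.

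| S | M | T | P1 | P2 | P3 | Cumulative |
|---|---|---|---|---|---|---|
| no | no | no | excluded | excluded | excluded | excluded |
| no | no | yes | excluded | excluded | excluded | AE |
| no | yes | no | excluded | excluded | excluded | AE |
| no | yes | yes | excluded | AE | AE | AE |
| yes | no | no | excluded | AE | excluded | AE |
| yes | no | yes | excluded | AE | AE | AE |
| yes | yes | no | excluded | AE | excluded | AE |
| yes | yes | yes | AE | AE | AE | AE |

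Here AE means only that this item does not remove the finding. The number of combinations excluded is 7, 3 and 5 of 8 under P1, P2 and P3, against 1 of 8 under the cumulative rule.

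The second and third rows carry the point. Every parse that keeps the *or* excludes them, and only the cumulative reading retains them:

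1. **Asymptomatic, treated, drug continued** (third row).
2. **Asymptomatic, untreated, drug stopped or delayed** (second row). A symptom-free ALT or AST value at or above 10 times ULN sits here if the withdrawal required by Protocol 9.7 ends study drug and no intervention is given.

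Following case 2 through the documents: 9.7 withdraws the patient; 9.1.1 says the finding is not an AE; 9.2 therefore does not collect it as one; SAP 8.1 and 8.3 have no record from which to form a TEAE; and the SAP 8.4 discontinuation table has nothing to count.

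I looked for text that would repair this. The procedures item in 9.1.1 rescues only a condition that necessitates a procedure. The sentence in 9.1.1 on clinically significant laboratory abnormalities concerns pre-existing conditions. The important-medical-event route in 9.1.2 reaches only events judged serious. None covers a non-serious case of type 1 or type 2.

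**The case against.** The strongest reply is that no sensible investigator would apply the sentence literally. The general definition is wide, the condition behind a procedure is kept as an AE, and blood dyscrasias without hospitalisation are given as an example of a possible SAE. All of this sits better with a cumulative reading. That is a fair account of the likely intention, but it is an argument for correcting the word. It also means that literal and purposive readings can coexist across sites.

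The second reply is that the data are not lost, and this largely stands. Laboratory values are a separate safety component. SAP 8.5 gives descriptive summaries, shift tables for critical chemistry and haematology tests, counts of ALT and AST at or above 3 times ULN and of bilirubin at or above 1.5 times ULN, and listings that include hepatic monitoring. A withdrawal and its reason would also appear in the SAP 5.1 disposition summary. These displays do not, however, carry the severity, relatedness and action taken that Protocol 9.2 requires for each AE.

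A reader might also infer more than the documents support:

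- *That symptomatic abnormalities are excluded too.* This depends on the parse; P2 keeps all of them as AEs.
- *That the conjunction is what keeps a merely monitored ALT rise out of the AE data.* With no symptoms, no intervention and drug continued, such a rise is excluded under the cumulative rule as well, unless monitoring itself counts as intervention. The protocol does not say whether it does.
- *That falls in fat-soluble vitamins are the events lost.* Protocol 9.1.1 separately keeps worsening EPI out of the AE data, so such falls may be excluded whatever the conjunction. Vitamins A, D, E and K are summarised in their own right in SAP 9.2.2.5.

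**Conclusion.** The sentence is wrong as written, in a limited way. Followed literally, it misclassifies asymptomatic laboratory abnormalities that are treated with drug continued, and those that stop or delay drug without being treated. Nothing elsewhere in the protocol or SAP corrects this for non-serious events.

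The consequence is a possible undercount of the AE/TEAE component, including the table of TEAEs leading to discontinuation, and possible inconsistency between sites. The documents give no frequency for such findings and no indication of how sites read the sentence, so the size is unknown.

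It would go too far to say that the primary safety endpoint as a whole is undercounted, because laboratory results form part of it and are reported regardless of AE status. Nor do the documents show a bias between treatments: the same rule applies in both periods of the crossover. The 10% in Protocol 10.2 is no yardstick for size either, since it is an upper confidence limit for an event not seen at all in 30 completers and not a threshold for observed AE rates.

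The conclusion assumes that the sentence is applied as written and, for the liver example, that withdrawal under 9.7 ends study drug without any other intervention.

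**What to change.** Reword the item in Protocol 9.1.1 along these lines: *Laboratory abnormalities that have no clinical manifestation AND require no medical intervention AND do not lead to termination or delay of study medication.*

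Reconcile it with 9.7 by stating whether hepatic monitoring alone counts as medical intervention for the purpose of AE recording. The rewording does not settle that question. Put the same text in the eCRF completion guide so that all sites apply one rule.

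The cost is about one sentence of protocol text, a clarifying line for 9.7, and a few more AE records. The sample size, the noninferiority margin, the efficacy analysis and the planned laboratory tables are unaffected.
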